5.0 Study Procedures

5.1 Study Design

Assessments

All patient-reported assessments will be conducted through the COAST platform. Additional data will be collected from participants' VA medical records (e.g., diagnoses, medications, service connection, service utilization). Assessments will occur at baseline ($T_0/ \sim T_{0+1\text{week}}$), post-treatment (T_1), and 3-months post-treatment (T_2) unless otherwise specified.

Study *feasibility* will be assessed by recruitment and intervention participation. Response to recruitment letters (# responses / # letters mailed) will be assessed overall and for each stratified group (age, sex, race). Participation will be assessed by number of enrolled participants that activate the COAST app, complete baseline assessments, engage in treatment beyond the initial recommendation, and complete the intervention.

COAST *usability* and *acceptability* will be measured with the Post-Study System Usability Questionnaire (PSSUQ).⁵⁹ The PSSUQ measures perceived satisfaction with a "system" like a website or mobile app. The PSSUQ is 16-items, scored 1-7 (1-strongly agree, 7-strongly disagree) or not applicable (N/A). The usability score is the average (total score divided by number of questions answered [N/A not included]). The three sub-scales are: usefulness (items 1-6), information quality (items 7-12), and interface quality (items 13-16). Lower scores, <3, indicate higher satisfaction and above average usability. The PSSUQ will be assessed at two time points. First, after the initial sleep/wake schedule recommendation is delivered ($\sim T_{0+1\text{ week}}$) as this will give participants a chance to learn the COAST platform and second, at T_1 , to measure change over time.

To further assess usability/acceptability, 15 Veterans will be interviewed (e.g., phone, Teams, VVC) to gain context on their COAST user experience and potential changes or new features that could improve COAST. Veterans will be interviewed based on their PSSUQ scores to get a range of perspectives, if available, per score distribution (e.g., 5 low, 5 medium, 5 high).

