The goal is to recruit and enroll 50 Veterans from VAPHS and affiliated CBOCs. Rather than recruiting in clinic and in-person, as is common for intervention trials such as this, to expand the pool of eligible participants we will primarily recruit through mail. The study team will mail a letter (see Recruitment Letters) to potentially eligible Veterans, based on inclusion and exclusion criteria, utilizing data from Veteran medical records. These letters will be sent from service line leaders at VAPHS—Behavioral Health, Primary Care, and Medicine (representing Sleep Medicine). A pre-screen list of potentially eligible Veterans will be generated by the study's data analyst, through VA's Corporate Data Warehouse, and stratified by sex (male/female), race (White/non-White), and age (<65/≥65) as an attempt to recruit a diversified sample. Then, letters will be mailed weekly to potentially eligible Veterans randomly selected from each stratified group (e.g., ~20-25/group). Letters will be sent until the goal of 50 Veterans have been enrolled.

Letters will ask Veterans to call the study coordinator for more information or they can return a letter indicating their interest. Interested Veterans who contact the study team will then schedule an eligibility screen (e.g., phone, Teams, VVC) with the study coordinator.

If feasible, depending on COVID-19 restrictions, recruitment will take place in VAPHS clinics (e.g., Primary Care, Behavioral Health, Sleep Medicine) in addition to the mail recruitment campaign. This may involve clinicians describing the study to their patients and providing study contact information as well as IRB approved fliers posted through VAPHS.

	White		Non-White		Total
	<65	≥65	<65	≥65	
Female	82	24	29	2	137
Male	346	859	48	65	1318
Total	1311		144		1455

As part of the proposal, a preparatory to research data query found VAPHS has n=1,455 Veterans who used sedative-hypnotic medications >14 doses/month for ≥3 months from 01/01/2019 to 01/31/2021 without diagnoses that would exclude

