them from participating. A new CDW query, using updated inclusion criteria, will update the pool of potential participants as of 1/31/2023. If feasible, depending on COVID-19 restrictions, recruitment will take place in VAPHS clinics (e.g., Primary Care, Behavioral Health, Sleep Medicine) in addition to the mail recruitment campaign. Clinicians familiar with the study can also notify the research team of interested, potentially-eligible participants via a research specific CPRS consult, so that a study member can contact a Veteran directly. This will minimize the burden on the clinician and help recruitment in clinical settings be more efficient.

Informed Consent Process

Interested Veterans who respond to the letter recruitment (or other methods) will be scheduled to undergo a screen (e.g., phone, Teams, VVC, in-person [only if necessary]) to confirm inclusion/exclusion criteria. The study team will also review their electronic medical record to confirm aspects of inclusion/exclusion criteria. If eligible, they will be invited to undergo the informed consent process via remote procedures (e.g., phone, Teams, VVC) or in-person if requested. For remote consent, Veterans will sign the ICF + HIPAA using DocuSign. If in-person, the Veteran will complete a written ICF + HIPAA.

Following consent, participants will be instructed on how to download the patient facing COAST app to their mobile device. Once downloaded, it will be activated with a unique code to prevent the app being used on another mobile device. Once the app is activated, the participants will be assigned a unique ID number, will undergo a brief training on how to use COAST, including instructions on how to access and navigate to the content areas, how to enter data for measures, how to use the sleep diary, and how to use the secure messaging. Previous testing of the COAST app by military Veterans and Service Members found its usability to be excellent and it received high scores for ease of use and learnability.⁵⁵ Since the initial development, the user interface has been further improved to meet the needs of users. Also, any technical issues with the app will be rapidly responded to by the study/Noctem team. After the app training, participants can then complete the baseline assessment in the COAST app.

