5.3 Data Analysis

This study is focused on the feasibility of recruitment and participation, usability and acceptability of COAST, and estimates of change in Veteran sleep and sedative-hypnotic use. The findings from this SPiRE will inform the study design of a larger clinical trial (e.g., RR&D Merit). A meta-analysis of digital CBT-I (2016) found a hedge's g of 1.09 (95% CI 0.74-1.45) when evaluating pre-post change on the Insomnia Severity Index (or similar measures).⁵⁴ The only study, to date, using NOCTEM COAST found a pre-post Cohen d of 1.93 for the ISI.⁵⁶ While there are few studies specifically looking at CBT-I plus sleep medication deprescribing, they show large effect sizes for change on the ISI (Cohen d = 1.98-2.26).^{49,64,65} Given the estimates from prior work conducted, we can expect an effect size range for pre-post ISI between 1.09 and 2.26 with an average effect size of 1.73 (large effect sizes). Given 50 recruited and accounting for a 25% drop out (i.e., 37 completers), we will still have 95% power to be able to detect an effect size of 0.65.

Prior to analyses for each aim, participant characteristics will be evaluated with descriptive statistics (e.g., age, sex, race). Distributions will be examined for normality, outliers, and missing data. Continuous variables (means/SD) and categorical variables (frequency/percentage) will be reported.

Aim 1. Feasibility will be evaluated in two ways. The first is by participant recruitment—how many participants contact the coordinator, undergo the study screen, and provide consent. The second is by treatment participation—how many participants download and activate the COAST app, complete baseline assessments, engage in treatment beyond the initial recommendation, and complete the intervention. Chi-square analyses will be used to determine group differences (age, sex, race) in recruitment response and participation rates.

Aim 2. Usability and acceptability of COAST will be evaluated by the PSSUQ measure. Usability/acceptability will be measured early in treatment ($T_{0+1\text{-week}}$) and at post-treatment (T_1) as well as change over time ($T_1 - T_{0+1\text{-week}}$). Change will be assessed using an intent-to-treat (ITT) approach and fitting mixed effects linear models that tests change in usability/acceptability (change on PSSUQ scores over the course of treatment) that includes a main effect of time ($T_{0+1\text{-week}}$ to T_1) and random effects for the Veteran.

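### Cheap improvement, not an error: add one age-sex-race model of letter response beside the single-factor chi-squares, because age and sex are strongly associated in the mailing list

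*Combined protocol and SAP*

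**What the plan says.** Section 5.1 (Assessments) defines the measure: "Response to recruitment letters (# responses / # letters mailed) will be assessed overall and for each stratified group (age, sex, race"). Section 5.2 (Recruitment Methods) builds a list stratified by sex, race (White/non-White) and age (under 65, 65 or over), "as an attempt to recruit a diversified sample". Each week, letters go to Veterans "randomly selected from each stratified group (e.g., ~20-25/group"), and "Letters will be sent until the goal of 50 Veterans have been enrolled". The preparatory table in that section shows eight cells of 2 to 859 Veterans, 1,455 in all. The counts will change: "A new CDW query, using updated inclusion criteria, will update the pool of potential participants as of 1/31/2023". Some participants may arrive without a letter, for instance: "Clinicians familiar with the study can also notify the research team of interested, potentially-eligible participants via a research specific CPRS consult".

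Section 5.3 (Aim 1) gives the test: "Chi-square analyses will be used to determine group differences (age, sex, race) in recruitment response and participation rates". Neither a joint age-sex-race model nor a rate weighted back to the pool is mentioned. The same section says: "The findings from this SPiRE will inform the study design of a larger clinical trial".

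**The concern.** Separate chi-squares for age, sex and race answer three marginal questions. If older and younger Veterans respond differently, and the men on the list are much older than the women, the sex test picks up part of the age difference. The next trial's team, wanting to know whom to approach differently, could attribute to sex what belongs to age.

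There is also a lesser point. Roughly equal weekly letters to very unequal cells over-represent the small cells by design. The crude overall response is then the yield of this mailing scheme, which need not equal the response rate of the eligible pool. A later trial that mails proportionally, or to everyone, would need the second figure to plan its number of letters.

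**Working it through.** **Inputs.** Cell counts N from the Section 5.2 table, in the order White <65, White ≥65, non-White <65, non-White ≥65: women 82, 24, 29, 2; men 346, 859, 48, 65. Letters: 25 per cell per week, the top of the plan's example range. Response and enrolment rates are assumed, because the documents give none.

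**The plan's own figure.** Women 82+24+29+2 = 137; men 346+859+48+65 = 1,318; total 1,455. White 1,311 and non-White 144. The table reproduces exactly.

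**Age by sex.**
- Whole pool: women ≥65 are (24+2)/137 = 26/137 = 19%; men ≥65 are (859+65)/1,318 = 924/1,318 = 70%.
- Letters per cell after w weeks are min(N, 25w). At w = 7: 82, 24, 29, 2, 175, 175, 48, 65, total 600. Women ≥65 are still 26/137 = 19%; men ≥65 are (175+65)/463 = 240/463 = 52%.

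**Sex comparison if only age matters** (assumed 5% under 65, 10% at 65 or over).
- Women: (111×0.05 + 26×0.10)/137 = 8.15/137 = 5.9%.
- Men, 600 letters: (223×0.05 + 240×0.10)/463 = 35.15/463 = 7.6%.
- Men, 1,455 letters: (394×0.05 + 924×0.10)/1,318 = 112.1/1,318 = 8.5%.

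Proportion of simulated trials with p<0.05 for sex (100,000 runs for the chi-squares, 5,000 for the model):

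| Test | 600 letters | 1,455 letters |
|---|---|---|
| Chi-square, uncorrected | 7.8% | 14.6% |
| Chi-square, Yates | 4.8% | 10.3% |
| Logistic, main effects of age, sex, race | 4.2% | 3.8% |

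A separate check with 15% under 65 and 8% at 65 or over, 22 letters per cell per week and 426 to 778 letters gave 11-13% for the uncorrected chi-square and 4-5% for the model.

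**Crude against pool-weighted rate.** Crude = Σ L·p / Σ L; pool = Σ N·p / 1,455, where L is letters and p the response rate in each cell. Assume White men ≥65 respond at 5% and everyone else at 10%, or the reverse, and that mailing stops at the first week with 50 expected enrolments.
- Pool rate: (859×0.05 + 596×0.10)/1,455 = 7.05%; reversed, 7.95%.
- Every responder enrols: 51.25/600 = 8.54%, a gap of +21%; reversed, 50/750 = 6.67%, a gap of −16%.
- 75% of responders enrol: 8.24% at 850 letters, +17%; reversed, 6.93% at 971, −13%.
- 50% enrol: 7.10% at 1,421 letters, +0.7%; reversed, 7.74% at 1,321, −2.6%.
- 40% enrol: 125 responses are needed, but the pool yields only 102.6 (115.7 reversed). All 1,455 are mailed and the gap is zero.
- With 8% against 10% the largest gap is about ±7%. With equal rates there is none.

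**Cost in precision.** When every responder enrols, the standard error of the weighted rate over that of the crude rate is 1.16/1.14 = 1.02 at 600 letters and 1.19/0.91 = 1.31 at 750 (reversed).

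**The case against.** A marginal sex difference in letter yield is a real difference among those mailed (5.9% against 7.6% in the example), so a significant chi-square is not a false positive for the question Section 5.3 asks. That stands. A reader might infer that the planned tests are invalid; the documents do not support this. The tests describe yield, and the gap is in attribution. With Yates correction the excess also disappears at 600 letters (4.8%), though not at 1,455 (10.3%).

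A reader might also infer that the crude response rate is biased, by as much as 21%. It is not biased for its own purpose, since the mailing is stratified on purpose and a trial repeating the scheme can use the crude yield directly. The 21% needs every responder to pass screening and consent. The budget in Section 4.0, with 25 baseline assessments in each of two years, also hints at prolonged mailing. If weekly mailing ran 24 weeks, 1,196 letters would have gone and the 5%/10% gap would be +6.3% or −5.6%. That is an inference, since mailing could pause.

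Finally, if the stratified groups in Section 5.1 are the eight mailing cells, the cell rates are already promised and only the weighting is missing. This too stands, and it is why the weighting is secondary.

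What the objections leave intact is the age-sex association, which no planned analysis separates.

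**Conclusion.** An optional improvement; nothing in the plan is wrong. The case for the joint model is the firmer part. It rests on the documents' own counts (19% of women against 52-70% of men aged 65 or over) and grows as more of the pool is mailed. Its practical size depends on an age effect that the documents do not quantify: under the 5%/10% assumption, about 8% to 15% apparent sex differences uncorrected, or 5% to 10% with Yates, against about 4% from the model.

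The weighted rate is conditional. It helps only if response varies by cell and mailing stops well short of the pool. The gap, at an assumed 5% against 10%, runs from +21%/−16% at the extreme to under 3% when half of responders enrol, and to zero when all are mailed. All figures use the preparatory counts, which the updated query will replace, and 25 letters per cell per week, which the plan gives only as an example.

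**What to change.** In Section 5.3, Aim 1:

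1. Keep the chi-squares, labelled as unadjusted. Add one logistic model of letter response on age, sex and race, main effects only.
2. Tally letters and letter responses by the eight mailing cells. Leave clinic, flyer and CPRS-consult referrals out of this analysis, since they have no letter denominator.
3. If mailing ends well before the pool is exhausted, report beside the crude yield the weighted rate Σ (N/N_total) × (cell response rate), using the updated CDW counts. Give a confidence interval, and merge the smallest cell with a neighbour (for example non-White women, 2+29 = 31).

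The cost is a few lines of analysis text and a tally from a list the study already builds; no new participant data are needed. The drawbacks are imprecision in the adjusted sex estimate (about 8 responses from women are expected under the 5%/10% age assumption) and a weighted rate whose standard error is about 1.0 to 1.3 times the crude one. Both rates should therefore be shown, neither replacing the other.

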The Insomnia Severity Index (ISI) will serve as the primary sleep outcome. The ISI is a brief measure of nighttime sleep disruption (e.g., severity of sleep onset) and daytime impact (e.g., interference with function).⁶⁰ The ISI is 7-items (0-4) with higher scores indicating greater severity or impairment. Total score (0-28) is categorized: no insomnia (0-7); sub-threshold (8-14); moderate (15-21); and severe insomnia (22-28). A reduction pre- to post-treatment ≥ 8 points indicate a treatment response and a post-treatment score ≤ 7 indicate remission. The ISI will be assessed at T₀, T₁, T₂ as well as weekly during treatment.

Sedative-hypnotic medication will be measured by participant self-report, as part of a daily entry in COAST (e.g., “What sleep medication and dose did you take today?”). The daily COAST entry will also involve assessments for adverse effects and/or withdrawal symptoms (i.e., Clinical Institute Withdrawal Assessment – Benzodiazepines [CIWA-B]). Outcomes will include post-treatment (T₁) medication dosage, relative to starting dose at baseline (T₀), and binary outcomes of $\geq 50\%$ reduction (yes/no) and total cessation (yes/no). Also, medication information from participants’ VA health records will be used to help validate their self-report of sedative-hypnotic use throughout the study. Additional information will be collected from the VA electronic health records (e.g., medical and psychiatric diagnoses, service utilization [e.g., insomnia-related care, behavioral health/sleep medicine appointments, sleep medicine pharmacy data]).

Additional *sleep* outcomes will be measured with a daily sleep diary.⁶¹ Sleep diaries provide information about a participant’s sleep behaviors, such as bedtime, rise time, total time in bed (TIB), total sleep time (TST), sleep onset latency (SOL), number of nighttime awakenings (NWAK), duration of wake after sleep onset (WASO), and sleep efficiency (SE). Sleep diaries will be completed daily from baseline (T₀) through post-treatment (T₁) and for 7-days at 3-month follow-up (T₂). Daily sleep diary data is used by COAST’s algorithms to generate personalized recommendations for each participant.

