Deprescribing/withdrawal risk. Deprescribing is the reduction or withdrawal of a medication managed by a healthcare professional that aims to reduce harm and improve outcomes. Veterans regularly engage in deprescribing for a variety of medications, including sedative-hypnotics, under the guidance of their health care providers (e.g., PCP, Clinical Pharmacist, etc.). When deprescribing sedative-hypnotics, rebound insomnia is common and expected. However, there is some risk for other withdrawal symptoms, which will be assessed daily (see below). For this study, deprescribing for each participant will be managed by study CPPs, licensed Clinical Pharmacy Specialists at VAPHS.

The deprescribing of sedative-hypnotics, while a common outpatient procedure, does impose risks such as rebound insomnia, the potential for more serious withdrawal symptoms, and psychological discomfort. As noted above in the inclusion/exclusion criteria, we have limited the sedative-hypnotics in this study to z-drugs (i.e., zolpidem, zaleplon, eszopiclone), trazodone, temazepam, and hydroxyzine as these represent the most commonly used medications for insomnia at VAPHS. Veterans who use other prescription medications to improve their sleep will not be excluded from this study; however, only z-drugs, trazodone, and temazepam will be targeted for deprescribing. Veterans who use over the counter medications for sleep will be managed on an individual basis. Also, for

Veterans taking zolpidem, trazodone, and temazepam at greater doses than is typically recommended,⁶³ their inclusion will be determined on a case by case basis. Any Veteran excluded but still interested in reducing their use of sedative-hypnotics will be referred to their prescribing provider for assistance. The study's CPPs will be responsible for the management of participants' sedative-hypnotics, including collaborating with participants' prescribing providers about who will enter the order in CPRS, communicating detailed instructions to participants and coordinating with them on the pick-up/delivery of medications, and, if necessary, the return of excess medication in higher doses. As needed, the study's CPPs will utilize clinical tools at her disposal to assist with an individualized taper, such as the VA Academic Detailing Benzodiazepine Tapering Calculator located on the VA Academic Detailing SharePoint.

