Veterans will be assessed for withdrawal symptoms and psychological discomfort (e.g., irritable, restless, anxious, fatigue) on a daily basis as part of the daily sleep diary entry through the COAST platform. First, Veterans will be asked if they are experiencing any unexpected symptoms (other than increased trouble sleeping, which is expected with medication reduction)? If so, Veterans will be prompted to complete the Clinical Institute Withdrawal Assessment – Benzodiazepines (CIWA-B) for more detailed information. Any participant report of withdrawal symptoms, psychological distress, and adverse effects will be reviewed by the study staff daily (during weekdays). If symptoms are reported outside of business hours, Monday-Friday (0800-1630 EST), reports will be reviewed on the next business day. After review of symptom reports, the study Clinical Pharmacist and/or Clinical Psychologists will contact the Veteran through the COAST platform's secure messaging to collect more information and provide feedback. As the study staff are only available during regular VA business hours (M-F, 0800-1630 EST), Veterans enrolled in the study will be instructed to contact emergency services if they ever feel they are experiencing emergent symptoms, study related or not. All Veterans will be provided the Veterans Crisis Line information as well. This approach to symptom management is similar to typical outpatient care at VAPHS.

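### The daily question that opens the CIWA-B asks only about unexpected symptoms, which is narrower than the withdrawal monitoring the protocol promises; delete that word

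*Combined protocol and SAP*

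**What the plan says.** The text is in section 5.1 of the combined protocol and SAP, under Potential Risks (deprescribing and withdrawal). It first separates two kinds of symptom. When sedative-hypnotics are reduced, "rebound insomnia is common and expected". The next sentence turns to everything else: "However, there is some risk for other withdrawal symptoms, which will be assessed daily (see below". Further down, the scope of monitoring is set: Veterans are to be assessed for "withdrawal symptoms and psychological discomfort (e.g., irritable, restless, anxious, fatigue) on a daily basis", within the COAST sleep diary entry.

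The mechanism has two steps. First, "Veterans will be asked if they are experiencing any unexpected symptoms (other than increased trouble sleeping, which is expected with medication reduction". Second, "If so, Veterans will be prompted to complete the Clinical Institute Withdrawal Assessment", in its benzodiazepine version (CIWA-B).

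The Assessments part of section 5.1 summarises the same daily step: "The daily COAST entry will also involve assessments for adverse effects and/or withdrawal symptoms (i.e., Clinical Institute Withdrawal Assessment – Benzodiazepines [CIWA-B". It does not mention the lead-in question and offers no other symptom question.

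Under Pharmacist-led Deprescribing, the taper may be paused at any time, either for withdrawal symptoms or because the participant is not coping with it. Withdrawal symptoms are to come in through COAST and be answered within one business day.

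**The concern.** The lead-in question decides whether the CIWA-B appears on a given day, and its key word is *unexpected*. The symptoms it is meant to find are ones the protocol itself foresees: psychological discomfort and more serious withdrawal symptoms are listed as risks of deprescribing next to rebound insomnia. The question therefore filters on whether the Veteran saw the symptom coming, when what matters is whether it is present.

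Some Veterans could plausibly read the item that way. The parenthesis justifies leaving out trouble sleeping because it is expected, and a Veteran could apply the same logic to anxiety or restlessness. The taper is individualised partly on how anxious the Veteran is about it, so the protocol anticipates participants who are anxious beforehand. Fatigue is described in the Introduction as a consequence of insomnia, so more of it may not feel surprising. These are inferences about how the item could be read. They are not evidence of how often it would be.

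At stake is withdrawal monitoring in a mostly remote taper, and the pause decisions that draw on it.

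**Working it through.** No arithmetic applies. The documents give no symptom rate, no sensitivity for the lead-in question and no CIWA-B threshold, so there is no figure to reproduce. The check is a comparison of texts in three steps.

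**Step 1: does the item cover its stated scope?** The table takes a Veteran's state on one day and asks whether the CIWA-B opens under three wordings of the lead-in question.

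| State that day | Within the stated daily scope? | Current item, read literally | *Unexpected* deleted | New or worse symptoms |
|---|---|---|---|---|
| Only increased trouble sleeping | No, carved out | No form | No form | No form |
| Restless, not anticipated, began today | Yes | Form | Form | Form |
| Anxious, anticipated, began today | Yes | May be no form | Form | Form |
| Anxious, anticipated, unchanged since earlier days | Yes | May be no form | Form | May be no form |

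The current wording can fail in the last two rows. Asking daily about new or worse symptoms repairs the third row but can fail in the fourth, because a continuing, unchanged symptom is neither new nor worse. Keeping the present-tense question about what the Veteran is experiencing, and removing only the one word, covers every row that is in scope.

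**Step 2: does another part of the protocol widen the item or schedule the CIWA-B without it?** The parts of 5.1 headed Assessments, Pharmacist-led Deprescribing, COAST Delivered CBT-I and Potential Risks were compared, together with 5.3. None gives a second daily symptom question or a CIWA-B that appears without the lead-in question. The deprescribing appendix that 5.1 points to is not in the text available for this check.

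**Step 3: does another scheduled measure do the same job?**
- PROMIS 29+2 includes Anxiety and Fatigue but has no schedule of its own, so it follows the default of baseline, post-treatment "and 3-months post-treatment (T_2) unless otherwise specified". It is an outcome measure, and its timing says nothing about how well the lead-in question works.
- The ISI is collected at those times "as well as weekly during treatment", but it measures insomnia and its daytime impact.
- The weekly C-SSRS is for eligible Veterans with suicidal ideation.
- The weekly assessments mentioned under COAST Delivered CBT-I are not described as a withdrawal screen.

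The item with its lead-in is therefore the only scheduled screen for non-sleep withdrawal symptoms that the documents describe.

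**Reach into the analysis.** Section 5.3 plans no analysis of CIWA-B data. The Aim 3 models use the ISI, sleep diary, PROMIS, dose reduction and cessation, and the power statement concerns the pre-post ISI effect. None of these uses the item.

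**The case against.** The strongest reply is that the sentence defines its own term. Trouble sleeping is the only symptom it names as expected, so everything else counts as unexpected. The opening of the same risk section draws the same line between rebound insomnia and other withdrawal symptoms. The sentence is also reported speech and not the app item itself, so the screen may already be worded more broadly.

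Nor is the daily question the only way in. Any report of withdrawal symptoms or distress is reviewed by staff each weekday. Secure messaging and appointments are available, the taper can be paused without a CIWA-B result, and Veterans are told to use emergency services for emergent symptoms.

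Most of this stands. The intent is clear, which makes this a correction of wording and not a missing safety procedure. The other routes are real, though they depend on the Veteran volunteering a problem, whereas the daily item asks. The intent argument also favours the edit, since removing the word makes the text say what its authors appear to mean.

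A reader might go further and infer that Assessments and Potential Risks contradict each other. They do not: the former summarises the daily step and leaves out the lead-in question. A reader might also infer that Veterans are told to expect anxiety or restlessness and so will routinely answer no. Nothing in the available text tells them so, and the consent pages are not available to check.

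**Conclusion.** The point holds as a cheap improvement. Read literally, the lead-in question is narrower than the daily monitoring that section 5.1 promises, and a Veteran who anticipated a symptom could truthfully answer no and not be shown the CIWA-B that day.

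The size is unknown. It depends on the on-screen wording and on how Veterans understand *unexpected*, and the documents show neither. No rate of missed reports is assumed here.

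The benefit is confined to withdrawal monitoring and taper-pause decisions. A reader might infer that withdrawal goes unmonitored, or that the efficacy results are biased. The documents support neither: monitoring is described with several routes, and no planned estimate, feasibility count or power figure changes.

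**What to change.** In section 5.1, Potential Risks, delete *unexpected* from the daily item. It should ask whether the Veteran is experiencing any symptoms other than increased trouble sleeping, whether or not they were expected. Keep the carve-out for trouble sleeping, which the daily diary and weekly ISI already follow. Do not ask about new or worse symptoms, for the reason given by the last row of the table.

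If the app item already omits the word, only the protocol sentence needs changing.

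The cost is one text edit, an app item edit if needed, and somewhat more CIWA-B forms for staff to review, including from Veterans with long-standing symptoms. The ceiling of one form per Veteran per diary day is the same under either wording.
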